10.4 Efficacy and toxicity definitions

Evaluable for toxicity. All patients will be evaluable for toxicity from the time of their first treatment with ponatinib.

Evaluable for objective response. Only those patients who have measurable disease per RECIST v 1.1. present at baseline, have received at least one dose of drug, and have had their disease re-evaluated will be considered evaluable for response. These patients will have their response classified according to the definitions stated below.

Best overall response. The best overall response is the best response recorded from the start of the treatment until disease progression/recurrence (taking as reference for progressive disease the smallest measurements recorded since the treatment started). The patient's best response assignment will depend on the achievement of both measurement and confirmation criteria.

Duration of response. The duration of overall response is measured from the time measurement criteria are met for CR or PR (whichever is first recorded) until the first date that recurrent or progressive disease is objectively documented (taking as reference for progressive disease the smallest

measurements recorded since the treatment started). The duration of overall CR is measured from the time measurement criteria are first met for CR until the first date that recurrent disease is objectively documented. The duration of stable disease is measured from the start of the treatment until the criteria for progression are met, taking as reference the smallest measurements recorded since the treatment started.

Progression-Free Survival. PFS is defined as the duration of time from start of treatment to time of progression. Because of the potential for CNS progression to reflect PK rather than biological reasons for progression, where possible CNS and extra-CNS PFS will also be recorded.

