- Based on literature data: FGFR1 SISH will be positive in 6% SCLC (no information available on ISH probability).
- RET will be positive in 2% adenocarcinomas. However, in a pan-negative adenocarcinoma/NOS population this is estimated at 20% based on internal data at CU and these patients will be prioritized internally for RET FISH testing after FGFR1 testing over those who have other markers positive.
- Based on literature data: ALK will be positive in 4% adenocarcinoma (excluded from testing in trial).
- Based on literature data (Western population): EGFR mutations will be positive in 10% adenocarcinoma (excluded from testing in trial)

We assume, for practical purposes, EGFR, ALK, RET and FGFR1 marker positivity will behave as if mutually exclusive.

We assume 85% of marker positive patients will enter treatment cohorts.

We assume 5% of patients will be non-evaluable on treatment.

To populate each cohort with 12 evaluable patients, therefore 15 positive patients need to be identified and 13 treated.

22 (20 evaluable) patient FGFR1 double negative cohort (up to additional 36 across all cohorts, but likely mostly within FGFR1 double negative cohort if altered dosing required)

13 patient FGFR1 SISH+ve and ISH+ve cohort

13 patient FGFR1 SISH+ve and ISH-ve cohort

13 patient FGFR1 SISH-ve and ISH+ve cohort

13 patient RET+ve cohort

This makes a total of 74 patients (inc non-evaluable) on the initial treatment study, with up to 100 if additional cohorts are added.

To populate these cohorts will require 700 patients to be screened for FGFR1 SISH and ISH and 266 by RET FISH.

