7.1.1 Updated vascular adverse event information

Arterial and venous thrombosis and occlusions, including fatal myocardial infarction, stroke, stenosis of large arterial vessels of the brain, severe peripheral vascular disease, and the need for urgent revascularization procedures have occurred in at least 27% of ponatinib-treated patients from the phase 1 and phase 2 trials. Ponatinib can cause fatal and life-threatening vascular occlusion within 2 weeks of starting treatment. Ponatinib can also cause recurrent or multi-site vascular occlusion.

In the dose-escalation (phase 1) clinical trial, 48% (31/65) of patients with CML or Ph+ ALL developed vascular occlusive events. The median time to onset of the first vascular occlusion event was 5 months.

Ponatinib can cause fatal and life-threatening vascular occlusion in patients treated at dose levels as low as 15 mg per day. Patients with and without cardiovascular risk factors, including patients age 50 years or younger, experienced these events. Vascular occlusion adverse events were more frequent with increasing age and in patients with prior history of ischemia, hypertension, diabetes, or hyperlipidemia.

Arterial Occlusion and Thrombosis

Arterial occlusion and thrombosis occurred in at least 20% (91/449) of Ponatinib-treated patients with some patients experiencing events of more than one type. Patients have required revascularization procedures (cerebrovascular, coronary, and peripheral arterial) due to vascular occlusion from Ponatinib.

Cardiac vascular occlusion, including fatal and life-threatening myocardial infarction and coronary artery occlusion has occurred in 12% (55/449) of Ponatinib -treated patients, Patients have developed heart failure concurrent or subsequent to the myocardial ischemic event.

Cerebrovascular occlusion, including fatal stroke has occurred in 6% (27/449) of Ponatinib -treated patients. Ponatinib can cause stenosis over multiple segments in major arterial vessels that supply the brain (e.g., carotid, vertebral, middle cerebral artery).

Peripheral arterial occlusive events, including fatal mesenteric artery occlusion and life-threatening peripheral arterial disease have occurred in 8% (36/449) of Ponatinib -treated patients. Patients have developed digital or distal extremity necrosis and have required amputations.

Venous Thromboembolism

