7.4 Planned efficacy assessments

Disease assessments (CT or PET/CT (including IV contrast if target lesions include those other than parenchymal lung lesions) encompassing all known sites of extra-CNS disease – if known brain metastases then additional baseline CNS imaging within the same time frame will also be considered as standard) will be performed at baseline (within 28 days prior to Cycle 1 Day 1) and then every other cycle (approximately every 8 weeks plus/minus 7 days) and response will be evaluated according to the RECIST criteria (version 1.1) (Appendix E). In order to accurately track the potential for new/progressive brain metastases on treatment, given the high potential for lung cancer to develop brain metastases, all patients must have had CT or MRI based brain imaging within 3 months of the planned start of treatment. Additional CNS imaging post-baseline in patients with known CNS metastases will be at the same interval as extra-CNS assessments, and in patients without known CNS metastases will be at the investigators discretion based on institutional practice and/or to assess symptoms suspicious of new/progressing CNS disease.

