10.0 ANALYSIS PLAN AND DATA CAPTURE

10.1 Estimated patient numbers

We aim to screen 700 patients in total in Part A (see Section 5 for details of calculation)

Study requirements, in terms of Part B enrollments: Accruing 13 patients for each 12 that will be evaluable.

22 (20 evaluable) patient FGFR1 double negative cohort (up to additional 36 across all cohorts, but likely mostly within FGFR1 double negative cohort if altered dosing required)

13 patient FGFR1 SISH+ve and ISH+ve cohort

13 patient FGFR1 SISH+ve and ISH-ve cohort

13 patient FGFR1 SISH-ve and ISH+ve cohort

13 patient RET+ve cohort

Estimate 74 patient (inc non-evaluable) on treatment study, up to 100 if additional biomarker cohorts are added to be explored.

Excess marker positive patients identified beyond the initial cohort accrual targets, will be directed towards additional expansion of cohorts (following additional support) if evidence of $ORR \geq 40\%$, other studies or remaining standard therapies as appropriate, while generating a larger natural history database relating to *FGFR1/RET* biology.

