10.3 Part B Analysis Plan

Sample size consideration:

The clinical trial will employ a one-stage design (A'Hern, 2001). In each molecularly defined positive cohort, the study requires 12 subjects to decide whether the ORR is greater than or equal to 0.400 assuming the response rate is 0.050 without treatment. 12 subjects will provide over 90% power to detect this rate difference with a targeted type I error rate of 0.05 and an actual error rate of 0.02. If the number of responses is 3 or more, the hypothesis that $P \leq 0.05$ (null hypothesis) is rejected. If the number of responses is 2 or less, the hypothesis that $P \geq 0.40$ is rejected. Note, given the exploratory nature of this phase II clinical trial, p-values will not be adjusted for multiple outcomes in the primary objective.

We will also include a pan-negative cohort of 20 patients to compare the ORR between each positive cohort and the negative one as secondary objectives. The ORR response differences between each biomarker positive cohort and the negative cohort will be evaluated using Fisher's exact test with a descriptive p-value. For *FGFR1* SISH+ or ISH+, the positive cohorts will also be combined for more power when comparing to the negative cohort. The response rates in different molecularly defined cohorts and different dose cohorts will be summarized using binomial proportions with 95% exact binomial confidence intervals. Differences among cohorts will be evaluated using Fisher's exact test with a descriptive p-value.

Another role of the double negative cohort is to permit rapid patient accrual to assess the PD/dose determination markers early in the conduct of the study, being expanded as needed if doses other than 45mg QD have to be explored. In addition, it may generate 'atypical' *RET* and *FGFR1* negative responders, to be further explored in future.

The proportion of the initial 12 patients at 45mg QD (and in the 12 patients at any subsequent dose levels) demonstrating a $\geq 50\%$ increase in plasma FGF23 by Day15 (defined as a 'PD-response') will be assessed in the same statistical manner as radiographic responses in order to determine whether the dose/regimen used is affecting the FGFR pathway in normal tissues. A $\geq 50\%$ increase in plasma FGF23 measurements occurring in ≥ 3 of 12 patients will be considered indicative of FGFR inhibition (Shi et al,

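### The primary per-cohort ORR leaves out treated patients who were never re-evaluated, so against all treated patients it can only be equal or higher

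*Combined protocol and SAP*

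**What the plan says.** Section 10.4 defines two sets. Every patient counts for toxicity from the first dose. For response, only patients with measurable disease at baseline who "have received at least one dose of drug, and have had their disease re-evaluated will be considered evaluable for response" count, and only these patients are given a response category.

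Section 7.4 schedules disease assessment at baseline and then "every other cycle (approximately every 8 weeks plus/minus 7 days".

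The sizing is built on the same set. Section 5.5 states "We assume 5% of patients will be non-evaluable on treatment", and section 10.1 plans on "Accruing 13 patients for each 12 that will be evaluable" and on a "22 (20 evaluable) patient FGFR1 double negative cohort". Section 10.3 says that "12 subjects will provide over 90% power to detect this rate difference", with 3 or more responses as success, and that response rates will be "summarized using binomial proportions with 95% exact binomial confidence intervals".

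No section counts a treated but unassessed patient as a non-responder, and no all-treated ORR analysis is planned. The closest text is at the end of section 10.3 (also in 4.0 and 9.3), which bases response rates on the number of patients treated at the final dose. That sentence applies only if doses other than 45mg are explored. It restricts by dose and does not clearly override section 10.4.

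**The concern.** ORR by cohort is the primary endpoint of Part B. Patients who leave before the first scan because of death, rapid deterioration or toxicity are treatment failures in any ordinary reading of a response rate. Under section 10.4 they can disappear from the calculation. The exclusion depends on outcome, because it can remove non-responders but never a recorded responder.

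Early loss is possible here. Section 6.1 admits platinum-pretreated patients with ECOG status up to 2, and section 7.1.1 warns that "Ponatinib can cause fatal and life-threatening vascular occlusion within 2 weeks of starting treatment". At stake is whether the published rate describes everyone exposed to the drug or only those who stayed long enough to be re-evaluated.

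**Working it through.** **Inputs.** n = 12, p0 = 0.05, p1 = 0.40, success at 3 or more responses (10.3). 13 treated per 12 evaluable, 22 per 20 (10.1). Non-evaluable 5% (5.5).

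**1. The plan's own figures reproduce.**
- Type I error: P(X ≥ 3 | 12, 0.05) = 1 − (0.5404 + 0.3413 + 0.0988) = 0.0196, stated as 0.02.
- Power: P(X ≥ 3 | 12, 0.40) = 0.9166, stated as over 90%.
- Accrual: 12/0.95 = 12.6, rounded up to 13; 20/0.95 = 21.1, rounded up to 22; 4 × 13 + 22 = 74.

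The design arithmetic is sound. The point concerns only the analysis set.

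**2. Direction.** Let r be responses, n treated, and k treated but never re-evaluated. The plan reports r/(n − k); the all-treated rate is r/n. Since r is the same in both, r/(n − k) ≥ r/n, strictly so when r ≥ 1 and k ≥ 1. The Clopper-Pearson limits behave alike: enumeration of every r and k for n from 2 to 39 found no case in which the estimate or either limit moved down.

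**3. Size with one of 13 lost.**

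| Responses | Re-evaluated set (n = 12) | All treated (n = 13) | Difference in estimate |
|---|---|---|---|
| 0 | 0% (0–26.5) | 0% (0–24.7) | none; only the upper limit moves |
| 3 | 25.0% (5.5–57.2) | 23.1% (5.0–53.8) | 1.9 points |
| 5 | 41.7% (15.2–72.3) | 38.5% (13.9–68.4) | 3.2 points |

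**4. How often anything changes.** At 5% independent loss, P(no loss among 13) = 0.95^13 = 0.513, so P(at least one) = 0.487.

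**5. The decision rule.** The plan does not say whether accrual stops at 13 treated or runs on to 12 evaluable, so both were checked for an all-treated response rate of 0.05.
- Accrual to 12 evaluable at 5% loss: the rate among evaluable patients is 0.05/0.95 = 0.0526, and P(X ≥ 3 | 12, 0.0526) = 0.0224.
- Exactly 13 treated: P(X ≥ 3 | 13, 0.05) = 0.0245. Power is 0.942 at an all-treated ORR of 0.40, and 0.923 at 0.38 (0.40 among evaluable × 0.95).

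Both error rates stay below the 0.05 target.

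**6. Sensitivity to the loss rate.** Here 40% and 5% are taken as all-treated rates, with accrual to 12 evaluable. Losses of 20% and 30% are assumptions; the documents give no such figures.

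| Loss d | A 40% rate reads 0.40/(1 − d) | P(≥ 3 of 12) when the all-treated rate is 5% |
|---|---|---|
| 5% | 42.1% | 0.0224 |
| 1/13 | 43.3% | 0.0242 |
| 20% | 50.0% | 0.0351 |
| 30% | 57.1% | 0.0492 |

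**The case against.** The strongest reply is that this is a prespecified choice of analysis set and not an error. The plan defines a response-evaluable set, sizes for it consistently, and attaches its 40% target to the 12 patients in it. On that view the all-treated figure answers another question: 40% among evaluable patients with 5% lost is 38% of all treated. This stands in part. The word bias applies only relative to all treated patients, and the plan is consistent with itself. But the set is conditioned on staying until re-evaluation, and loss through death, progression or toxicity is unlikely to be unrelated to response.

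The shift is also small: 1.9 to 3.2 points inside intervals about 52 to 57 points wide, in a trial the plan calls exploratory. That stands, and it limits the weight of the point.

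A reader might infer from the vascular warning that early losses will be large. The documents do not support this. Section 7.1.1 gives no rate for the first 2 weeks and puts the median onset of the first occlusive event at 5 months. Section 2.3 notes that this falls well after the 8-week assessment. Section 6 requires a life expectancy of at least 3 months and excludes prior infarction, stroke and thrombo-embolism.

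Section 10.4 does not define re-evaluation, and section 9.5 recognises clinically documented progression. If clinical progression before a scan counts as re-evaluation, fewer patients are lost. The direction is the same, and a patient who dies before any assessment is still left out.

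**Conclusion.** The point holds. Relative to all treated patients with measurable disease, the primary ORR and its exact interval are never lower and sometimes higher: by about 2 points at 3 responses and 3 points at 5 responses when one of 13 is lost. With no responses only the upper limit rises, and at 5% loss about half of cohorts show no change. This rests on counting unassessed treated patients as non-responders and, for the frequency, on independent losses at the protocol's 5%.

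Three stronger conclusions might be drawn, and the documents support none of them.
- **That the success rule is compromised.** It is a count of responses, and its type I error is 0.0196, 0.0224 or 0.0245 depending on how accrual ends.
- **That the comparison with the double negative cohort is tilted in favour of the markers.** The same exclusion applies to both sides. With illustrative counts of 5/13 against 1/22 the ratio is 8.5; losing one positive-cohort patient gives (5/12)/(1/22) = 9.2, and losing two double negative patients gives (5/13)/(1/20) = 7.7. The direction is not determined.
- **That expansion decisions at an ORR of 40% are inflated.** This would follow only if 40% means an observed rate. The plan does not say so, and it may mean the rule of 3 or more responses.

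**What to change.** In sections 10.3 and 10.4, and in the synopsis where it repeats them, define the primary ORR and its exact interval on all patients with measurable baseline disease who received at least one dose. Count those with no post-baseline disease assessment as non-responders. Apply this in every cohort, including the double negative one. Keep the re-evaluated set as a named sensitivity analysis. Reconcile the new wording with the sentence in section 10.3 that uses the number treated at the final dose, so that one denominator rule applies whether or not other doses are explored.

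The sample size and the rule of 3 or more responses can stay as they are. The cost is an amendment to the definition of the primary analysis set, with no extra patients. The reported ORR may be slightly lower.

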responses are seen in the initial RET+ cohort but FGFR1+ responses or FGFR PD modulation have been noted at 45mg and 45mg appears acutely well tolerated per DLT criteria we will reconsider this logic and accrue an additional RET+ cohort at 45mg. If doses other than 45mg QD are explored, the number of patients in each biomarker selected cohort will be modified to include only those treated at the final ‘biologically selected dose’ (i.e. the tolerable dose associated with evidence of FGFR pathway pharmacodynamic modulation or of radiographic responses in FGFR biomarker selected cohorts) and the response rates in each biomarker selected cohort will be calculated within each cohort using only the number treated at this dose.

Objectives:

Primary:

Part A – To determine the prevalence of defined biomarkers in the screened patient populations.

Part B – To determine the objective response rate (ORR) (RECIST v1.1) to ponatinib at a ‘biologically selected dose’ in different molecularly defined cohorts of lung cancer.

Secondary:

Part A –

- 1) To determine the effectiveness of prescreening locally and nationally.
- 2) To determine the clinical and pathological features associated with biomarker positivity and negativity.

Part B –

- 1) To evaluate the safety, tolerability, and adverse event profile of ponatinib in patients with advanced lung cancer.
- 2) To determine the progression free survival (PFS), pattern of failure (CNS vs. extra-CNS) and response duration (in patients who achieve an objective response) of ponatinib in molecularly defined cohorts of patients with advanced lung cancer treated at the ‘biologically selected dose’.
- 3) To compare the ORR in biomarker positive cohorts to the FGFR1 double negative cohort.

Tertiary/Exploratory:

- 1) To explore additional molecular mechanisms of initial sensitivity and resistance to ponatinib in patients with advanced lung cancer, including but not limited to addressing the impact of higher cutpoints/alternate patterns of FGFR1 copy number by SISH and mRNA levels by ISH on maximal percentage shrinkage per RECIST or PFS or duration of response in the FGFR1 copy number and/or mRNA positive cohorts; and the impact of FGF2 and/or 9 ligand mRNA levels by ISH on maximal percentage shrinkage per RECIST or PFS or duration of response in FGFR1 copy number and/or mRNA positive cohorts.

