2009). In addition, FGFR inhibition should be accompanied with a decrease in the fractional excretion of phosphorus in the urine (normal: 10-15%) and an elevation of serum phosphorus compared to baseline at the same time. If exposures are inadequate to affect these biomarkers (provided no evidence of tumor shrinkage has occurred in any of the FGFR+ cohorts by that point), due to the new data on risk factors associated with ponatinib, higher doses/dosing regimens of ponatinib will not be explored, however, if 45mg is not tolerable, but there is insufficient evidence to assess efficacy, 30mg will be considered for exploration in the FGFR-related cohorts. RET patients will commence at 30mg from the start due to the higher potency for ponatinib towards RET. A dose level will be considered tolerable following completion of 1 cycle (28 days) in 9 of 12 patients in the absence of dose limiting toxicity (DLT). If ≥ 3 patients experience DLT at this dose level, the dose level will be deemed non-tolerated.

If doses other than 45mg QD have to be explored, the number of patients in each biomarker selected cohort will be modified to include only those treated at the final 'biologically selected dose' (i.e. the dose associated with evidence of FGFR pathway PD modulation or of radiographic responses in FGFR+ cohorts) and the response rates in each biomarker selected cohort will be calculated within each cohort using only the number treated at this dose. The number of adverse events and percentages will be tabulated per organ and per visit. Kaplan-Meier survival curves will be used to display PFS and extra-CNS PFS (Camidge et al, 2011; Lin et al, 2012). Progression-free median time and 95% confidence interval will be reported. Proportions of failure due to CNS or extra-CNS will be reported along with 95% exact confidence intervals. Response duration will be summarized using median and range (min, max). Where biomarker overlap occurs, exploratory analyses of the differential effect of one biomarker over another will be explored across patients in all cohorts using multivariate analysis. Exploratory analyses will include assessing the impact of different SISH+ patterns, of higher cutpoints for FGFR1 SISH and ISH and the impact of FGF ligand levels on maximal percentage shrinkage per RECIST or PFS or duration of response in the FGFR1 SISH/ISH+ cohorts.

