Partial Response (PR):

At least a 30% decrease in the sum of diameters of target lesions, taking as reference the baseline sum diameters.

Progressive Disease (PD):

At least a 20% increase in the sum of diameters of target lesions, taking as reference the smallest sum on study (this includes the baseline sum if that is the smallest on study). In addition to the relative increase of 20%, the sum must also demonstrate an absolute increase of at least 5 mm. (Note: the appearance of one or more new lesions is also considered progression).

Stable Disease (SD):

Neither sufficient shrinkage to qualify for PR nor sufficient increase to qualify for PD, taking as reference the smallest sum diameters while on study.

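### Section 10.4 ends PFS and response duration at progression only, so the endpoint is time to progression labelled PFS; handling of ongoing responses is not stated

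*Combined protocol and SAP*

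**What the plan says.** PFS and response duration make up most of Part B secondary objective 2: "To determine the progression free survival (PFS), pattern of failure (CNS vs. extra-CNS) and response duration" (section 1). They are also outcomes in the exploratory cutpoint and ligand analyses of section 10.3.

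The definitions are in section 10.4. For PFS: "PFS is defined as the duration of time from start of treatment to time of progression". Response duration runs from first meeting the criteria for CR or PR "until the first date that recurrent or progressive disease is objectively documented". The definition for complete responses alone has the same form, ending at documented recurrence.

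The analyses are in section 10.3. For PFS: "Kaplan-Meier survival curves will be used to display PFS and extra-CNS PFS", and "Progression-free median time and 95% confidence interval will be reported". For response duration the whole plan is: "Response duration will be summarized using median and range (min, max"). The synopsis repeats these sentences. No censoring rule is given for either endpoint.

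**The concern.** A definition that stops at progression leaves a patient who dies first without an event. The analyst must then censor or drop that patient, and either choice treats the death as uninformative about failure. The usual purpose of PFS is to count such a death as a failure.

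Deaths of this kind are possible here. The first scheduled reassessment is at about 8 weeks (section 7.4), and the updated risk text in section 2.2.2 says that fatal vascular occlusion can occur within 2 weeks of starting. A patient who dies before any reassessment is also outside the response denominator, because only those who "have had their disease re-evaluated will be considered evaluable for response" are counted there. Under the current wording such a death counts against the drug in neither ORR nor PFS, and would show only in safety or survival data.

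Separately, a median and range taken on raw durations has no valid place for a response that is still ongoing at analysis, and the plan does not say what to do with one.

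**Working it through.** **1. Does any other text bring death in?**

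- Appendix E defines progressive disease by measurement, "At least a 20% increase in the sum of diameters of target lesions" with an absolute increase of at least 5 mm, or by new lesions. Death is not included.
- Section 9.5 lists progression as discontinuation reason 1 and death as reason 5, so the protocol treats them as different things.
- Sections 4.0 and 5.3 plan to capture overall survival, but do not link it to PFS.

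Nothing adds death. Read literally, section 10.4 defines time to progression.

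**2. The plan's own figure.** No event count or power is given for PFS or response duration. The only related design figure is the ORR rule in section 10.3: n = 12, at least 3 responses, null 0.05, target 0.40. By the exact binomial:

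- Type I error: 1 − (0.5404 + 0.3413 + 0.0988) = 0.0196, matching the stated 0.02.
- Power: 1 − (0.0022 + 0.0174 + 0.0639) = 0.917, matching the stated value of over 90%.

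Neither quantity involves the PFS definition.

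**3. Size of the PFS bias (illustrative).** Assume constant hazards, k of 12 patients whose first event is death without progression, and those deaths censored at the date of death. With q = k/12 and total hazard λ, the true median PFS is ln 2/λ. The median with deaths uncounted is ln 2/[(1 − q)λ]. The ratio is 1/(1 − q).

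| k of 12 | Ratio | Overstatement |
|---|---|---|
| 1 | 12/11 = 1.091 | 9% |
| 2 | 12/10 = 1.200 | 20% |
| 3 | 12/9 = 1.333 | 33% |

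For scale, if all events are observed, an approximate 95% CI for an exponential median multiplies and divides it by exp(1.96/√d). That factor is 1.76 for d = 12, and 1.39 for d = 36 (three FGFR1-positive cohorts of 12 evaluable patients).

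**4. Effect of the scan schedule.** The formula treats progression time as continuous, but progression would be dated at 8-weekly scans. Simulating cohorts of 12 on that grid, with one uncounted death placed evenly in weeks 0–8, leaves the Kaplan-Meier median unchanged in about 73%, 56% and 44% of cohorts when the median time to progression is 2, 4 and 6 months. In the rest it moves up. With three such deaths it usually moves at 4–6 months. The bias is real but lumpy.

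**5. Response duration (constructed example).** Take five responders at 2, 4, 5+, 8+ and 10+ months, where + means ongoing. The raw median of all times is 5, and of completed responses only it is 3. The Kaplan-Meier curve is 0.8 at month 2 and 0.6 at month 4, then falls no further, so its median is not reached. If the 8-month response had ended, the raw median of all times would still be 5, while Kaplan-Meier gives 0.6 × 1/2 = 0.3 at month 8 and a median of 8.

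**The case against.** *PFS is understood to include death.* By convention, yes, but the protocol writes out a definition that omits it. If the convention was meant, the text is wrong; if progression only was meant, the label is.

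*Some of these patients may already have an event.* Discontinuation reason 1 in section 9.5 covers clinical as well as radiological progression, and the PFS sentence does not require objective documentation. A patient who declines and dies between scans might be dated as progressed. This stands in part: the same item ties progression to RECIST 1.1, so the point is unsettled, and Appendix E gives only highlights of that guideline. It would reduce the number of uncounted deaths but would not cover sudden ones.

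*Early deaths may be rare.* Section 6.1 requires a life expectancy of at least 3 months and ECOG 2 or better, section 6.2 excludes prior infarction, stroke and thrombo-embolism, and section 2.2.2 gives a median onset of 5 months for vascular occlusion. The phase I summary there reports 8 deaths among 81 patients over a median of 54 weeks, in a different disease. All of this stands: the frequency is unknown, and 3 of 12 would be high.

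*The response-duration wording does not exclude a Kaplan-Meier median.* Correct. A reader might infer that a raw median is prescribed. The text does not say so. It names Kaplan-Meier for PFS, does not name it for response duration, and leaves ongoing responses unaddressed. That is a gap in specification, not a stated wrong method.

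*Little depends on it.* PFS and response duration carry no test, threshold or go/no-go rule. This limits the severity but does not make the definition right.

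**Conclusion.** The PFS definition is wrong as written for an endpoint of that name, and the response-duration definition has the same omission. If deaths without documented progression occur and are censored when they happen, the reported median PFS can only be too long or unchanged. The 9%, 20% and 33% rest on assumed death counts, constant hazards and continuous progression times. In a single cohort they lie well inside the sampling uncertainty (a factor of 1.76), but the bias does not shrink if cohorts are combined.

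Two stronger readings are not supported. A reader might infer that median PFS will be inflated by some large, definite amount; the documents give neither the number nor the timing of such deaths, so no figure can be forecast. A reader might also infer that the primary ORR conclusion is affected. The 3-of-12 rule, its type I error of 0.0196 and its power of 0.917 do not depend on the PFS definition; who is evaluable for response is a separate matter.

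The consequence is confined to secondary objective 2 and the exploratory analyses that use these outcomes. It should be fixed before analysis.

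**What to change.** In section 10.4:

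- Define PFS as first dose to the earlier of RECIST progression or death from any cause.
- Censor patients without an event at their last evaluable disease assessment.
- State a rule for deaths after new anti-cancer therapy or after missed assessments. Without one, a patient who stops for toxicity and dies much later would enter as a late event, which could itself lengthen PFS.
- End response duration at progression or death, and say how death is handled in extra-CNS PFS.
- If progression only is intended, rename the endpoint time to progression here, in the objectives and in section 10.3.

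In section 10.3 and the synopsis, specify a Kaplan-Meier median for response duration, with ongoing responses censored and flagged in the reported range.

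**Cost.** A few sentences; n, type I error and power of the ORR test do not change. Death dates should come from the survival capture in sections 4.0 and 5.3. That source needs confirming, because section 4.0 ties later analysis to available funding and the study calendar has no survival visit after first progression. The SAE route in section 9.5 is not enough alone, since deaths more than 30 days after the last dose are reported only when thought drug-related. Reported PFS may be shorter. Response-duration estimates will be imprecise: a cohort of 12 yields about 12 × 0.40 = 4.8 responders at the target rate and 12 × 0.05 = 0.6 at the null.
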